We will test for adjusted mean differences between groups, typically via covariate-adjusted least square comparisons. Covariates will include age, gender, and IQ and, nested within the gene-carrier group, CAG length and its interaction with age. We will adjust for potential group differences in residual variances, and if substantial violations of test-assumption data distributions are noted we will adjust the analyses by outcome-variable transformation if possible. Failing this, we will use nonparametric bootstrapping for inference and confidence level estimation. In secondary analyses, we will assess correlations between outcomes and the CAP statistic that has proved a powerful

predictor of HD progression in older participants (Ross et al., 2014). We will assess longitudinal neurodegeneration using mostly linear models with participant random effects. Broadly, we will compare the premanifest gene carriers to controls and test disease burden influence within the CAG-expanded. We will protect against multiple comparison and reporting bias by designating a limited set of primary outcomes based upon established relevance to HD and high measurement reliability (e.g., NfL, putamen volume). We will calculate family-wise error and false discovery rates (FDR) for these measures. We will group all other outcomes by measurement class (e.g., serum assays) and report FDR estimates per class. In the event of substantial missing predictor data, we will use multiple imputation. We will subject critical data with plausible informative missingness to sensitivity analyses. All analyses will be prespecified in the Statistical Analysis Plan prior to initiation of data analysis.

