Huntington's Disease Young Adult Study 2.0

5th December 2023

HD-YAS 2.0 SAP 5th December 2023

Overview:

The Huntington's Disease Young Adult Study (HD-YAS) is part of the Wellcome Trust funded TREAT-HD programme, which aims to deliver therapies to prevent neurodegeneration in HD. In parallel to exploring novel therapeutic strategies in HD, HD-YAS aims to identify the optimum time window to deliver preventative treatments. Specifically, it seeks to determine early systems-level pathology in very early premanifest HD gene carriers, and to assess the impact of this degeneration on symptomatology. From 2017 to 2019 a cohort of 64 premanifest HD gene carriers approximately 24 years from expected symptom onset and 67 matched controls underwent clinical, cognitive, neuropsychiatric, neuroimaging and biofluid assessments (Scahill *et al*, 2020). There was no evidence of disease-related functional impairment. No significant differences in brain structure and function were evident between gene carriers and controls with the exception of smaller striatal volumes. Neurofilament light (NfL), a marker of neuronal damage, was elevated in gene carriers, with higher levels in those closest to expected symptom onset. HD-YAS 2.0 provides follow up approximately 4.5 years after baseline with the aim of determining whether ongoing longitudinal degeneration is evident and whether this impacts function. We will determine this by addressing the following hypotheses:

Hypothesis 1: There is evidence of a disease-related measurable phenotype ~20 years from expected symptom onset in:

- a) brain imaging;
- b) cognition;
- c) neuropsychiatric function; and
- d) biofluid measures.

Hypothesis 2: There is evidence of disease-related *longitudinal* change ~20 years from expected symptom onset in:

- a) brain imaging;
- b) cognition;

- c) neuropsychiatric function; and
- d) biofluid measures.

Hypothesis 3: Early pathological events lead to impairment in isolated functional domains such as cognitive flexibility.

Hypothesis 4: Individuals with higher levels of somatic CAG-repeat expansion are more vulnerable to early striatal atrophy, breakdown of corticostriatal connections and cortical pathology.

Hypothesis 5: Measures identified as showing disease sensitivity in hypotheses 1 and 2 have utility for future trials of disease-modifying therapy in premanifest HD gene carriers.

The Cohort

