Violation of model distribution assumptions

For the default general linear models, the key standard assumptions are that residuals of the outcome variable will be approximately normally distributed, independent of the predicted values, and with uniform variance. The assumption is most commonly violated when the residuals show notable skewness. In such cases we will first evaluate whether the assumptions are reasonably satisfied by a square-root, log, polynomial, or inverse

transformation of the outcome, in which cases the analysis will proceed with the transformed variable. Such transformations are most commonly unsatisfactory due to floor or ceiling effects in the range of measurement of the outcome. In such cases we will consider the feasibility of using an ordinal logistic model or a censored model. If neither of these is practical and satisfactory, then the model will be subjected to bootstrapping as described above for outliers. If residual variance changes systematically by value of a covariate (e.g. age) then we will fit the models using iteratively reweighted least-squares, with weighting based on the relevant covariate.

Multiple testing

The issue of multiplicity in outcomes will be addressed by calculating estimated false discovery rates (FDR) for the covariate-adjusted difference between premanifest HD gene carriers and controls. We will perform the FDR analyses at the domain level. (Rigor is not diminished by performing these calculations at the domain level rather than in a single appraisal of the combined domains. Unlike correction for family-wise error rate, FDR calculations depend on the distribution but not on the number of hypothesis test p values considered simultaneously.) One cognitive measure, the CANTAB *inter-extra dimensional shift* task (IED), will be treated as a confirmatory rather than exploratory analysis, based on previous data showing HE differences far from onset. Significance tests will be taken at face value for this test, and it will not be included in the false discovery corrections.

Hypothesis Testing

Hypothesis 1: There is evidence of a disease-related measurable phenotype ~20 years from expected symptom onset in: a) brain imaging; b) cognition; c) neuropsychiatric function; and d) biofluid measures.

A repetition of the cross-sectional analyses performed in HD-YAS 1.0 will be performed, using the additional statistical power provided by the repeated or new subject

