$$\begin{aligned} & \text{follow-up} * (a_1 + a_2 * \text{CAG} + a_3 * \text{age} + a_4 * \text{CAG} * \text{age}) + \\ & \text{follow-up} * (a_5 * \text{baseline biomarker}) + a_6 * \text{biomarker change from baseline}, \end{aligned}$$

Hypothesis 4: Individuals with higher levels of somatic CAG-repeat expansion are more vulnerable to early striatal atrophy, breakdown of corticostriatal connections and cortical pathology.

We will analyse potential relationships between somatic expansion and other HD measures using the same models described immediately above for hypothesis 3.

Hypothesis 5: Measures identified as showing disease sensitivity in hypotheses 1 and 2 have utility for future trials of disease-modifying therapy in premanifest HD gene carriers.

We will calculate nominal sample size estimates for longitudinal measures showing relationship to HD gene expansion vs. controls or longitudinal relationships to the severity of combined age and CAG genetic risk. We will perform such calculations for measures with longitudinal change below the 15% estimated false discovery rate. We note however, that this screening for evidence of disease sensitivity will tend to optimistically bias such estimates towards smaller sample sizes. The resultant sample sizes will therefore represent an estimated lower bound.

We will consider the following 5 biomarkers as primary outcomes for these analyses, as previous data, including baseline data from YAS 1 have suggested cross-sectional relationships between these measures and early HD disease pathology:

1. Putamen volume change
2. Caudate volume BSI
3. CSF NfL levels
4. Plasma NfL levels

5. CSF mHTT levels

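### For Hypothesis 1, the imaging and biofluid FDR families include outcomes that HD-YAS 1.0 already found to differ, which can loosen the cut-off for the exploratory outcomes beside them

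*SAP*

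**What the plan says.** The SAP (General Methods, Multiple testing) handles multiplicity by "calculating estimated false discovery rates (FDR) for the covariate-adjusted difference between premanifest HD gene carriers and controls", and adds: "We will perform the FDR analyses at the domain level". The one exception is the CANTAB IED task, which is treated as confirmatory because of earlier data and kept out of the FDR calculation.

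The SAP's Overview reports on HD-YAS 1.0: "No significant differences in brain structure and function were evident between gene carriers and controls with the exception of smaller striatal volumes". It also says: "Neurofilament light (NfL), a marker of neuronal damage, was elevated in gene carriers". Table 1 lists putamen and caudate under neuroimaging, and CSF and plasma NfL under biofluid markers. Hypothesis 1 is then tested as follows: "A repetition of the cross-sectional analyses performed in HD-YAS 1.0 will be performed", on the baseline data plus the new measurements.

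Protocol section 8 describes a different arrangement. A limited primary set, with NfL and putamen volume as examples, has its own family-wise error and FDR. For the rest: "We will group all other outcomes by measurement class (e.g., serum assays) and report FDR estimates per class". In the SAP a primary set appears only under Hypothesis 5, for the sample-size work.

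**The concern.** In a step-up FDR procedure every rejection raises the threshold for the remaining p values. Outcomes that were positive on the baseline rows, and are retested on data containing those rows, are likely to be rejected again. The exploratory outcomes in the same family are then judged more leniently than they would be alone. The SAP defends domain-level families by noting that FDR depends on how the p values are distributed rather than on their number. That dependence is the mechanism here, because adding very small p values changes the distribution.

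The reported FDR would be correct for the mixed list. Readers, however, will take the new claims from the exploratory part: connectivity, NODDI, MPM, tau, GFAP and so on. Those results also feed forward, since Hypothesis 3 is limited to measures that show carrier-control differences under Hypotheses 1 and 2.

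**Working it through.** **The plan's own figure.** The documents give no error rate for exploratory findings. The nearest design figure is the baseline power statement in protocol section 8 (60 per group, 0.53 SD, 5 covariates, 80%). A noncentral t calculation with 113 degrees of freedom and a variance inflation of 1/(1 − 5/119) gives 80.4%, so it reproduces. It is not the number at issue.

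**Inputs.**
- Imaging family (Table 1, cross-sectional): 6 volumes + 20 connectome (6 + 14) + 5 NODDI + 3 MPM = 34.
- Biofluid family: 7 CSF + 4 plasma = 11. Mutant HTT and somatic expansion have no carrier-control test, and total HTT was not measured at this visit.
- Known positives k, imaging: 2 if "with the exception of smaller striatal volumes" covers both putamen and caudate; 1 if protocol section 8 is right that only the putamen differed.
- Known positives k, biofluid: 2, assuming NfL was raised in both fluids. The Overview names no fluid.
- FDR level q: assumed 5% to 15%. The only level in the SAP belongs to Hypothesis 5: "We will perform such calculations for measures with longitudinal change below the 15% estimated false discovery rate".
- Rule: Benjamini-Hochberg, assumed.

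**Threshold.** With k sure rejections among m outcomes, the best of the m0 = m − k exploratory outcomes is compared with (k + 1)q/m. In a family of its own it would be compared with q/m0. For imaging with k = 2 this is 3q/34 against q/32. At q = 5% it is 0.0044 against 0.0016.

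**Chance of any false exploratory finding, all exploratory outcomes null and independent.** The first step alone gives 1 − (1 − (k + 1)q/m)^m0. Simulation of the full step-up rule (at least 100,000 runs) adds a little. In a separate family the chance is q.

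| Family | q | First step by formula | Simulated, mixed | Ratio to q |
|---|---|---|---|---|
| Imaging, k = 2 | 5% | 13.2% | 13.3% | 2.7 |
| Imaging, k = 2 | 15% | 34.7% | 35.3% | 2.4 |
| Imaging, k = 1 | 5% | 9.3% | 9.4% | 1.9 |
| Imaging, k = 1 | 15% | 25.4% | 26.2% | 1.7 |
| Biofluid, k = 2 | 5% | 11.6% | 11.7% | 2.3 |
| Biofluid, k = 2 | 15% | 31.3% | 31.9% | 2.1 |

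Repeat runs moved these by a few tenths of a point.

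**Relaxing the assumptions.**
- Correlation 0.5, at q = 5% and 15%: imaging k = 2, 8.4% and 20.4% (1.7 and 1.4 times q); imaging k = 1, 6.1% and 15.7% (1.2 and 1.05 times q); biofluid, 8.9% and 23.4% (1.8 and 1.6 times q).
- Known positives with only about 80% unadjusted power, independent outcomes: 1.7 to 1.8 times q for k = 2, and 1.4 for k = 1.
- Some exploratory outcomes real (about 80% unadjusted power, independent, k = 2). Here the measure is the FDR within the exploratory set. Imaging: 1.8 to 2.1 times q with one real, 1.3 to 1.5 with three, 1.0 to 1.1 with six. Biofluid: 1.4 to 1.7 with one real, 0.8 to 0.9 with three.
- A family with no known positive (cognition without IED): 1.0.

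FDR over the whole family was at or below q in these simulations.

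**Reuse of rows.** Baseline has 64 carriers and 67 controls; 57 and 45 returned; 9 and 14 are new. For within-person correlation of 0.3 to 0.95, the baseline and pooled test statistics correlate at 0.79 to 0.92. An outcome with no true effect that reached p < 0.05 at baseline would do so again in the pooled test 43% to 62% of the time. This is a separate scenario from the table, which takes the known positives as near certain.

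**The case against.** The strongest reply is that nothing formal is broken. Domain-level FDR is controlled for the family as defined, and the SAP regards everything except IED as exploratory. If striatal volume and NfL are rejected again, the imaging and biofluid parts of Hypothesis 1 are answered yes whatever the exploratory outcomes show. All of this stands. A reader might infer that the SAP's FDR control fails, or that the Hypothesis 1 conclusions in these domains are unsound. The documents support neither.

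A reader might also infer that false exploratory findings simply become twice as likely. That needs no real exploratory effects, roughly independent outcomes and near-certain known positives. Imaging and biofluid measures are likely to be correlated. The protocol's reference list also includes a cross-sectional report from this cohort whose title refers to altered iron and myelin, so treating every MPM outcome as null is doubtful. The factor is therefore a range.

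The list of known positives is partly assumed too, for caudate and for the NfL fluid. The SAP describes Hypothesis 1 as a repetition with more power and does not claim independent confirmation, so the row-reuse figure is a caution for reporting and not an error in the plan.

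What survives is the inconsistency. The protocol separates established outcomes from the rest, and the SAP does so for IED because of earlier data, but not for outcomes with earlier data from this very cohort.

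**Conclusion.** The point holds as a conditional one for two of the four Hypothesis 1 domains. In the imaging and biofluid families, outcomes already reported as different loosen the cut-off for the exploratory outcomes.

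With no real exploratory effects and independent outcomes, the chance of a false exploratory finding is about 1.7 to 2.7 times q. For imaging that means 9% to 13% at q = 5% and 26% to 36% at q = 15%; for biofluid, about 12% and 32%. It moves towards q, or below it, under correlation, weaker known positives or several real effects.

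These sizes rest on a Benjamini-Hochberg rule, an assumed q and the assumed list of known positives. Both documents report no other baseline imaging difference, so few real imaging effects is a reasonable planning case. This is a cheap improvement to the plan and does not invalidate it.

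**What to change.** In the SAP's multiple-testing section, for Hypothesis 1:

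1. Place the outcomes already positive in HD-YAS 1.0 in a separate primary family with its own family-wise error and FDR, as protocol section 8 describes. Putamen volume and NfL belong there. Include caudate, and each NfL fluid, only if the sponsor confirms that it was positive at baseline; the protocol and the SAP should be reconciled on caudate.
2. Report these outcomes with confidence intervals as updated estimates, and say that their pooled p values are not independent confirmation of HD-YAS 1.0.
3. Compute the imaging and biofluid FDR over the remaining outcomes only.
4. State the FDR procedure and level that apply to Hypothesis 1.

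This takes a short SAP edit and no new data. The cost is a somewhat stricter cut-off, and so some loss of power, for exploratory outcomes in the two domains.

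### The SAP omits the protocol's family-wise calculation for a designated primary set, and its claim that domain-level FDR costs no rigour does not hold study-wide

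*SAP*

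**What the plan says.** Protocol section 8 (Data Analysis) guards against multiplicity and reporting bias by "designating a limited set of primary outcomes based upon established relevance to HD and high measurement reliability", with NfL and putamen volume as examples. Three commitments follow:

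- for the primary set: "We will calculate family-wise error and false discovery rates (FDR) for these measures";
- for the rest: "We will group all other outcomes by measurement class (e.g., serum assays) and report FDR estimates per class";
- for both: "All analyses will be prespecified in the Statistical Analysis Plan prior to initiation of data analysis".

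The SAP's Multiple testing section calculates FDR, domain by domain, for the covariate-adjusted carrier-control difference. It mentions family-wise error only as a contrast, in a parenthesis stating that "Rigor is not diminished by performing these calculations at the domain level rather than in a single appraisal of the combined domains". The reason given is that "FDR calculations depend on the distribution but not on the number of hypothesis test p values considered simultaneously". The IED task is treated as confirmatory, tested at face value and left out of the FDR.

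Under Hypothesis 5 (H5) the SAP says "We will consider the following 5 biomarkers as primary outcomes for these analyses": putamen volume change, caudate BSI, CSF NfL, plasma NfL and CSF mHTT. No family-wise step is attached. H5 also screens measures for sample-size work at a 15% estimated FDR.

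**The concern.** There are two separate problems.

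**A commitment is missing.** For Hypotheses 1 and 2 (H1, H2) the SAP names no primary set and no family-wise calculation. The H5 list cannot stand in. It is primary only for the sample-size analyses, and one of its members, mHTT, is tested in carriers only and so has no carrier-control p value. IED does not fill the gap either: it carries no family-wise calculation and does not cover putamen or NfL. The SAP does not explain the change.

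**The rigour sentence claims too much.** It compares domain-level FDR with one appraisal of all domains together, so it is a statement about the study as a whole. For a fixed distribution of p values its supporting reason is true. Splitting by domain, however, changes the distribution within each family. A domain with no true effect can still produce discoveries, and all of them are then false.

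The results feed forward. H3 is limited to measures that differ between carriers and controls, and H5 screens at 15%. The SAP's caveat in H5 is about optimistic sample sizes, not about how many screened measures are false. A reader of the rigour sentence could take domain-level values as study-wide rates.

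**Working it through.** **The protocol's own figure.** With 60 per group, 0.53 SD and 5 covariates, the noncentrality is 0.53 × √(60 × 60/120) = 2.90 on 120 − 2 − 5 = 113 df. Power at two-sided 5% is 82%. With a variance inflation of 1 + 5/112 = 1.045 for the covariates it is 80.4%, which agrees with the printed 80%. The documents derive no multiplicity figure.

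**Tests with a usable carrier-control change, counted from Table 1**

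- Imaging: 6 volumes (each once) + 20 connectome + 5 NODDI + 3 MPM = 34.
- Cognitive: 16 − 4 IED variables (all taken as outside the FDR) − Goals Prior (new at this visit) = 11.
- Neuropsychiatric: 18.
- Biofluid: 14 − mHTT − total HTT − somatic expansion = 11.
- Clinical 1, Functional 2.

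The four domains of H1/H2 give 34 + 11 + 18 + 11 = 74 tests. The six headings of Table 1 give 77.

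**Assumptions.** Benjamini-Hochberg (BH; the SAP names no estimator), the 15% level, independent t tests, 57 carriers and 45 controls (the returners in the SAP's cohort section), and d = 0.53 borrowed from the protocol's cross-sectional calculation. Noncentrality is 0.53 × √(57 × 45/102) = 2.66 on 95 df. True effects lie only in imaging and biofluid, which is a sparse pattern like the striatal and NfL differences reported at baseline. 57/45 is an upper bound for imaging and CSF, since 91% of the cohort had MRI and 86% had CSF.

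**Why the union exceeds 15%.** With two true effects in each of imaging and biofluid, BH gives a within-domain FDR of 0.15 × 32/34 = 14% and 0.15 × 9/11 = 12%. Each domain without a true effect has a 15% chance of a false discovery. For the two such domains among four, the chance of at least one is 1 − 0.85² = 28%. For the four among six headings it is 1 − 0.85⁴ = 48%. A single pooled BH over 74 tests has FDR 0.15 × 70/74 = 14%.

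**Simulated study-wide FDR (20,000 replicates)**

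| True effects (imaging + biofluid) | Four domains | Six headings | Pooled |
|---|---|---|---|
| 1 + 1 | 34% | 44% | 15% |
| 2 + 2 | 27% | 33% | 14% |
| 5 + 3 | 19–20% | 23% | 13–14% |
| 10 + 5 | 13% | 15–16% | 12% |

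Repeat runs of the 2 + 2 row gave 26–27% for four domains. Mean false measures in that row are 1.1, 1.5 and 0.5. With within-domain correlation of 0.3 to 0.5 the row becomes 26%, 33% and 12–14%. With d = 0.3 or 0.8 in place of 0.53 it is 39% or 22% (four domains), 51% or 26% (six headings) and 14% pooled.

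**Family-wise step for four outcomes in H2 (57/45, 0.53 SD).** Power per outcome is 75% for an unadjusted 5% test and 55% at 0.05/4 = 0.0125. Holm over four outcomes gives 55% when one effect is true and 65% when all four are (100,000 replicates). With four true effects, BH within imaging at 15% detects putamen about 48% of the time.

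**IED.** At face value, and if the tests are independent, the chance of a false positive is 5% for one variable and 1 − 0.95⁴ = 18.5% for the four in Table 1.

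**The case against.** Four objections carry weight.

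**Domain-level FDR follows the protocol.** The protocol itself plans FDR per measurement class for non-primary outcomes. A reader might infer that splitting by domain is the departure. It is not: the departure is the absent primary set and family-wise calculation. Each domain's FDR also remains valid in its own right, so a pooled FDR is not required.

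**Nothing shows that putamen or NfL get an easier test.** A reader might infer that dropping the family-wise step lowers the bar. In the four-effect scenario Holm detects putamen more often (65%) than imaging-domain BH at 15% does (48%). What is lost is a promised kind of error statement, not necessarily stringency.

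**27–33% is not the H5 error rate.** The illustration covers only carrier-control tests. H5 also admits measures through a longitudinal relationship with age and CAG severity, which is not modelled. Its outputs are nominal best-case sample sizes, and no confirmatory claim rests on them.

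**A family-wise statement for H1 has a limit.** H1 pools both visits (64 + 9 = 73 carriers, 67 + 14 = 81 controls) and reuses baseline data in which putamen and NfL differences were already seen. Adjusted p values there would not account for that selection. The clean family-wise claim is mainly for H2.

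All four stand and narrow the point. None supplies the missing calculation or makes the rigour sentence true for the study as a whole.

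**Conclusion.** The point holds on both parts. The first is textual and needs no simulation: for H1 and H2 the SAP has no counterpart to the protocol's primary set with family-wise error. The second holds as a general statement: control within each domain does not carry over to the union of domains. The size depends on how sparse the effects are. At 15% with four true effects, the study-wide rate is about 26–27% (four domains) or 33% (six headings), against 14% pooled. With about 15 true effects the excess is nearly gone. These figures rest on BH, the assumed number, location and size of effects, and 57/45. They are robust to the within-domain correlation tried. The gap between four and six groups also shows that the undefined term *domain* matters: with six, Clinical holds a single test (Total Motor Score), whose adjusted value equals its raw p value.

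**What to change.** (a) In the SAP, designate the primary set for the longitudinal carrier-control tests (H2), for example putamen, caudate, CSF NfL and plasma NfL, and report Holm-adjusted p values beside the FDR. mHTT cannot join, because it is tested in carriers only. If the set is also used for H1, state that H1 reuses baseline data in which putamen and NfL differences were already seen, so its adjusted p values do not account for that selection. State that IED is a separate confirmatory test outside this family, so the 5% family-wise level does not cover it.

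(b) Replace the rigour sentence with: *Domain-level FDR applies within a domain and is not a study-wide rate.* Repeat this at the 15% screen in H5.

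(c) State whether the domains are the four in H1/H2 or the six headings of Table 1. Keep domain-level FDR for all other outcomes.

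Cost: SAP wording and one column of adjusted p values, with no new data and unchanged FDR results. On the family-wise scale, power per H2 outcome is about 55–65%. The 75% comparator is an unadjusted 5% test, which the SAP does not apply to these outcomes.
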